12.1 Patient numbers and power considerations

The aim of the randomization is to evaluate whether addition of targeted fludarabine results in a reduction of the incidence of severe viral infections. For the primary endpoint, patients will be considered a success if they did not develop serious infections within 100 days posttransplant while being alive, relapse-free. Based on the retrospective data, we hypothesize that 40 % of the subjects treating according to arm A will experience serious infections. To detect a 25% reduction of failures with arm B with a power of 80%, each arm should consist of 42 patients evaluable at day 100. This is based on the assumption that 10% of patients in each arm will not contribute to the primary analysis due to death or relapse. This leads to an assumed proportion of failures of 40/90=0.4444444 in arm A and 15/90=0.1666667 in arm B (2-sided significance level of 0.05, Z test with pooled variance, power=81%). To compensate for non-evaluability due to death, relapse or other reasons, 15% extra patients per arm will be included, leading to a total sample size of 2 times 49, is 98 patients.

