12.4.1 Primary endpoint

The primary endpoint is the probability of serious viral infections up to 100 days after transplantation for patients alive relapse-free at 100 days. This endpoint will be analyzed in a poisson regression model including treatment arm and the stratification factors used in the randomization.

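### Section 12.4.1 names Poisson regression for a yes/no endpoint without a robust variance; with the default model-based variance, power at 42 evaluable per arm is about 66–70%, against the 81% that 12.1 gives for a pooled Z test

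*Protocol*

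**What the plan says.** Section 12.4.1 defines the endpoint as a probability among a subset of patients: "The primary endpoint is the probability of serious viral infections up to 100 days after transplantation for patients alive relapse-free at 100 days". It then names the analysis: "This endpoint will be analyzed in a poisson regression model including treatment arm and the stratification factors used in the randomization". Section 10.3.2 gives one stratification factor, creatinine clearance above 90 ml/min or below, with 1:1 allocation.

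Section 12.1 sizes the trial as a comparison of two proportions. The target is "To detect a 25% reduction of failures with arm B with a power of 80" per cent, with an assumed "proportion of failures of 40/90=0.4444444 in arm A and 15/90=0.1666667 in arm B". It concludes that "each arm should consist of 42 patients evaluable at day 100", with the test given as "2-sided significance level of 0.05, Z test with pooled variance, power=81" per cent. On losses it assumes that "10% of patients in each arm will not contribute to the primary analysis due to death or relapse", and it enrols 49 per arm.

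Neither section says whether the Poisson standard errors are model-based or robust. Neither links the Z-test power to the Poisson model.

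**The concern.** Poisson regression sets the variance of each observation equal to its mean, p. A yes/no outcome has variance p(1−p). When events are rare the two nearly agree. At the planned rates of 17% and 44% they do not: the Poisson value is larger by a factor of 1/(1−p), which is 1.2 in arm B and 1.8 in arm A. Unless the variance is corrected, standard errors are too large, confidence intervals too wide and the test too conservative.

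Standard software uses the model-based variance unless told otherwise, so a literal fit of 12.4.1 would have this defect. At stake is the power of the only primary comparison in a 98-patient trial. The choice could also decide the result. Take 18/42 against 8/42 failures, a little short of the planned effect:

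- Pooled Z: difference 10/42 = 0.238, SE 0.101, p = 0.018.
- Robust Poisson: log(18/8) = 0.811, SE √(1/18 + 1/8 − 2/42) = 0.365, p = 0.026.
- Model-based Poisson, Wald: the same 0.811, SE √(1/18 + 1/8) = 0.425, p = 0.056.

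**Working it through.** **Inputs.** From section 12.1: pA = 40/90 = 0.4444, pB = 15/90 = 0.1667, n = 42 evaluable per arm, two-sided 0.05. Also from 12.1: 49 enrolled per arm less 10% leaves 49 × 0.9 = 44.1, about 44.

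**1. The plan's own figure.** For the pooled Z test the mean rate is 0.3056.

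- Pooled SE = √(2 × 0.3056 × 0.6944/42) = 0.1005.
- Unpooled SE = √((0.4444 × 0.5556 + 0.1667 × 0.8333)/42) = 0.0958.
- Power = Φ((0.2778 − 1.96 × 0.1005)/0.0958) = Φ(0.843) = 80.0%.

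Summing exactly over both binomial distributions gives 80.9%. The stated 81% is reproduced.

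**2. Standard error of the log risk ratio at the planned rates.** Expected failures are 42 × 0.4444 = 18.67 and 42 × 0.1667 = 7.

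- Model-based Poisson: √(1/18.67 + 1/7) = 0.443.
- Binomial, which the robust variance estimates: √(1/18.67 + 1/7 − 2/42) = 0.386.
- Ratio 0.443/0.386 = 1.15.

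For a risk ratio of 0.1667/0.4444 = 0.375, the 95% interval is 0.16 to 0.89 with the first and 0.18 to 0.80 with the second.

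**3. Power, exact enumeration over two binomials, no stratum term.**

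| Evaluable per arm | Pooled Z | Poisson model-based, Wald | Poisson model-based, likelihood ratio | Poisson robust |
|---|---|---|---|---|
| 42 | 80.9% | 65.9% | 69.6% | 78.3% |
| 44 | 83.2% | 68.5% | 71.8% | 80.9% |
| 49 | 86.2% | 74.2% | 76.9% | 84.3% |

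The model-based Wald test needs about 55 evaluable per arm for 80% power, more than the 49 enrolled. A normal approximation on the log scale is lower for both variances at 42 per arm (61% model-based, 72% robust). The exact figures are used because they do not rest on that approximation.

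**4. Two-sided type I error at 42 per arm, common rate 0.306.** Pooled Z 5.1%, model-based Wald 1.6%, model-based likelihood ratio 2.1%, robust 4.1%.

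**5. With the stratum term.** The protocol gives neither the split between strata nor the stratum risks. Assuming a 50/50 split and stratum risks either equal or 30% above and below the arm rate, 5,000 simulated trials per setting at 42 per arm give 66–67% (model-based Wald), 69–70% (likelihood ratio) and 79–80% (robust). Adjustment barely changes the picture over that range.

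**The case against.** The strongest objection is that the protocol never says the variance is model-based. Poisson regression with a robust variance is a recognised way to estimate an adjusted risk ratio for a binary outcome, so naming Poisson is not in itself an error. The variance estimator is a detail that a statistical analysis plan, not shown here, may settle. This stands. A reader might infer that the trial simply has 65–70% power; the document does not support that, because the figure depends on a choice it leaves open.

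Second, a reader might infer that 81% is a miscalculation. It is not: it reproduces for the test that 12.1 names. Sizing on a simple two-proportion test and analysing with an adjusted model is also common practice, and is not by itself a contradiction.

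Third, the 42-per-arm figures are for the smallest denominator in the plan. At the 44 expected after 10% loss, robust Poisson has 80.9% power, in line with the stated value.

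Fourth, the error is conservative. It costs power and precision but does not raise the risk of a false positive.

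What remains is that 12.1 states power for one test and 12.4.1 names another, with no link between them. Fitted as literally written with software defaults, the named model falls clearly short of the stated power. That is more than a missing detail.

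**Conclusion.** The point holds conditionally. The 81% in 12.1 is right for the pooled Z test, but it is not the power of the analysis named in 12.4.1. Under model-based variance, power is about 66–70% at 42 evaluable per arm and 68–72% at 44, standard errors are about 15% too large, and the type I error is about 2% instead of 5%. Under robust variance, power is about 78% at 42 (79–80% with the stratum term) and 81% at 44, so the shortfall is small or absent.

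These figures rest on the protocol's own failure rates. The stratum-adjusted ones also rest on the assumed split and risks stated above. The protocol does not support saying that the trial is underpowered as it stands, or that Poisson regression is the wrong model. It supports saying that the variance must be named before the analysis and that the power statement should refer to the same test.

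**What to change.** In 12.4.1, specify Poisson regression with robust (sandwich) variance, adjusted for the creatinine-clearance stratum. A stratified Cochran-Mantel-Haenszel test on the same stratum is an acceptable alternative and is close in form to the Z test used for sizing, but changing to it is optional. In 12.1, state the power of whichever test is chosen.

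The cost is one sentence, one option in the code and possibly a slightly lower stated power, about 78–80% at 42 evaluable per arm with the robust variance. No extra patients, visits or data are needed.

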12.4.2 Secondary endpoints

All time-to-event endpoints are measured from the date of stem cell infusion. Cumulative incidence of aGVHD grade II-IV is to the time to aGVHD II-IV at day 100 with relapse and death as competing events. A 95% confidence interval will be constructed. Overall survival (OS) is defined as the probability to be alive. EFS is defined as the time interval of being alive without relapse/disease progression or graft failure. Relapse incidence (RI) is defined as probability of relapse/progression, with death as a competing event. Non-relapse mortality (NRM) is defined as probability of death without relapse or progression. Time to engraftment will be analysed as a competing risks outcome with competing event death without engraftment.

OS and EFS will be estimated by the Kaplan-Meier product method. Competing risks outcomes will be estimated by cumulative incidence curves and will also utilize models based on cause-specific hazard models. 95% confidence intervals will be constructed.

12.4.3 ATG and fludarabine exposure

ATG and fludarabine exposure will be measured as cumulative exposure, which will be correlated to immune reconstitution and clinical outcome.

12.4.4 Toxicity analysis

The analysis of treatment toxicity will be done primarily by tabulation of the incidence of adverse events and infections with CTCAE grade 3 or 4, excluding AEs as outlined in 11.2.2.

13. ETHICAL CONSIDERATIONS

13.1 Regulation statement

The study will be conducted according to the principles of the Declaration of Helsinki 1964 (last amended by the 64th WMA General Assembly in October 2013) and in accordance with the Medical Research Involving Human Subjects Act (WMO) and Good Clinical Practice. The accredited EC will approve the study protocol and any substantial amendments.

13.2 Recruitment and consent

After referral for allo-SCT, for each patient the best treatment and donor will be discussed in a SCT meeting. For patients eligible to the inclusion criteria of this study, this study will be considered as one of the options. If a benefit is argument in favor of this study and this $\alpha\beta$ TCR/CD19 depleted allo-SCT protocol is considered to be the best option, the responsible SCT doctor will discuss the treatment proposal with the patient. This is always done during the second visit.

Written informed consent of patients is required before enrolment in the trial and before any study related procedure takes place.

The investigator will follow ICH-GCP and other applicable regulations in informing the patient and obtaining consent. The investigator should take into consideration if the patient is capable of giving informed consent. Before informed consent may be obtained, the investigator should provide the patient ample time and opportunity to inquire about details of the trial and to decide whether or not to participate in the trial. All questions about the trial should be answered to the satisfaction of the patient.

There is no set time limit for the patient to make a decision. The investigator should inform each patient if there is a specific reason why he/she must decide within a limited time frame, for example if patients condition necessitates start of treatment or if the trial is scheduled to close for enrolment.

The content of the patient information letter, informed consent form and any other written information to be provided to patients will be in compliance with ICH-GCP and other applicable regulations and should be approved by the Ethics Committee in advance of use. The patient information letter, informed consent form and any other written information to be provided to patients will be revised whenever important new information becomes available

that may be relevant to the patient's consent. Any revised informed consent form and written information should be approved by the Ethics Committee in advance of use. The patient should be informed in a timely manner if new information becomes available that might be relevant to the patient's willingness to continue participation in the trial. The communication of this information should be documented.

13.3 Benefits and risks assessment

13.3.1 Burden

The protocol comprises a different dosing of fludarabine in the experimental arm. In addition, extra blood (9 times 45 ml) and bone marrow (4 times 5 ml) will be sampled for exploratory endpoints. Sampling will take place at moments blood or bone marrow sampling was scheduled for routine clinical care. The intervals of sampling are > 1 month. The average blood volume in humans is 4.5 – 5.6 liter. We don't expect that donation of maximum 1% of the total blood volume will lead to cytopenias and/or an increase of bloodtransfusions. Bone marrow sampling for exploratory endpoints will always be executed after bone marrow has been sampled for clinical monitoring.

All other acts, measurements, follow-up and level of care are similar to off-study patients undergoing allo-SCT. The burden of the therapy is associated with the allo-SCT itself, which is a necessary therapeutic intervention in all subjects.

13.3.2 Risks

Possible increased risks for the recipient are graft failures, though not observed so far in all cohorts with the intended dose levels. The intended target level of fludarabine remains in the range of all so far treated patients at the UMCU. We only propose to avoid too high exposure to fludarabine.

13.3.3 Benefits

Possible benefits include a proposed lower incidence of infections as well as optimized cancer surveillance due to a more balanced immune reconstitution.

13.4 Compensation for injury

The sponsor (UMCU) has a liability insurance which is in accordance with article 7 of the WMO.

The sponsor (also) has an insurance which is in accordance with the legal requirements in the Netherlands (Article 7 WMO). This insurance provides cover for damage to research subjects through injury or death caused by the study.

- 1. € 650.000,-- (i.e. six hundred and fifty thousand Euro) for death or injury for each subject who participates in the Research;
- 2. € 5.000.000,-- (i.e. five million Euro) for death or injury for all subjects who participate in the Research;
- 3. € 7.500.000,-- (i.e. seven million five hundred thousand Euro) for the total damage incurred by the organization for all damage disclosed by scientific research for the Sponsor as 'verrichter' in the meaning of said Act in each year of insurance coverage.

The insurance applies to the damage that becomes apparent during the study or within 4 years after the end of the study.

14. DATA COLLECTION AND QUALITY ASSURANCE

14.1 Electronic Data Capture (EDC)

Data will be collected on electronic Case Report Forms (eCRF) in the EDC system to document eligibility, safety and efficacy parameters, compliance to treatment schedules and parameters necessary to evaluate the study endpoints. Data collected in the EDC system are derived from the protocol and will include at least:

- inclusion and exclusion criteria;
- baseline status of patient including medical history and stage of disease;
- timing and dosage of protocol treatment;
- (severe) adverse events;
- parameters for response evaluation;
- any other parameters necessary to evaluate the study endpoints;
- survival status of patient;
- reason for end of protocol treatment.

The eCRFs will be completed on site by the local investigator or an authorized staff member. Each eCRF must be dated and signed by the local investigator upon completion. All eCRF entries must be based on source documents. The eCRF and instructions for completing the eCRF will be provided by the UMC Utrecht Hematology data-management.

14.2 Monitoring

Independent monitors of the Julius Clinical BV will perform on-site monitoring visits to verify that trial conduct at the site is in compliance with ICH-GCP and the applicable regulatory requirements, as depicted in the 'monitoring plan'.

According to the NFU risk classification, we consider the risk as 'moderate'. As stated before, the greatest hazard for the patient is determined by the allo-SCT as such. Additional side

effects may be an increased risk of graft failures or GVHD, though not observed so far in all cohorts with the intended dose levels. The intended target level of fludarabine remains in the range of all so far treated patients at the UMCU. We only propose to avoid too high exposure to fludarabine. Blood and bone marrow sampling for biological studies are not expected to induce any side effects.

15. ADMINISTRATIVE ASPECTS AND PUBLICATION

15.1 Handling and storage of data and documents

15.1.1 Patient confidentiality

Each patient is assigned a unique patient study number at registration. In trial documents the patient's identity is coded by patient study number as assigned.

The local investigator will keep a subject enrolment and identification log that contains the key to the code, i.e. a record of the personal identification data linked to each patient study number. This record is filed at the investigational site and should only be accessed by the investigator and the supporting site staff, and by representatives of the sponsor (UMCU) or a regulatory agency for the purpose of monitoring visits or audits and inspections.

15.1.2 Filing of essential documents

Essential Documents are those documents that permit evaluation of the conduct of a trial and the quality of the data produced. The essential documents may be subject to, and should be available for, audit by the sponsor's auditor and inspection by the regulatory authority(ies). The investigator should file all essential documents relevant to the conduct of the trial on site. The sponsor (UMCU) will file all essential documents relevant to the overall conduct of the trial. Essential documents should be filed in such a manner that they are protected from accidental loss and can be easily retrieved for review.

15.1.3 Record retention

Essential documents should be retained for 15 years after the end of the trial. They should be destroyed after this time.

Source documents (i.e. medical records) of patients should be retained for at least 15 years after the end of the trial. Record retention and destruction after this time is subject to the site's guidelines regarding medical records.

15.1.4 Storage of samples

Biological samples should only be stored for the purpose of additional research if the patient has given consent. If no informed consent was obtained, samples should be destroyed after the patient has completed all protocol treatment and procedures.

Storage of biological samples on site is subject to the site's guidelines; samples are stripped from any identifying information and labelled with a code (trial name or number and patient study number as assigned at enrolment).

15.1.5 Disclosure of an extract of the data with Miltenyi Biotec

Miltenyi Biotec has developed the Clinimacs ® TCR α / β Product line for graft engineering. For post marketing research, Miltenyi will receive an extraction of the data obtained in this study from subjects which have given consent. Applicable Data Privacy Laws will be followed. The dataset will contain data with regards to clinical outcome, immuno reconstitution and graft composition. Data cannot be linked to participants of this study.

15.2 Amendments

A 'substantial amendment' is defined as an amendment to the terms of the EC application, or to the protocol or any other supporting documentation, that is likely to affect to a significant degree:

- the safety or physical or mental integrity of the subjects of the trial;
- the scientific value of the trial;
- the conduct or management of the trial; or
- the quality or safety of any intervention used in the trial.

All substantial amendments will be notified to the EC and to the competent authority.

Non-substantial amendments will not be notified to the accredited EC and the competent authority, but will be recorded and filed by the sponsor (UMCU).

15.3 Annual progress report

The sponsor (UMCU) will submit a summary of the progress of the trial to the accredited EC once a year. Information will be provided on the date of inclusion of the first subject, numbers of subjects included and numbers of subjects that have completed the trial, serious adverse events/ serious adverse reactions, other problems, and amendments.

15.4 End of study report

The sponsor (UMCU) will notify the accredited EC and the competent authority of the end of the study within a period of 90 days. The end of the study is defined as the last patient's last visit.

The sponsor will notify the EC immediately of a temporary halt of the study, including the reason of such an action.

In case the study is ended prematurely, the sponsor will notify the EC and the competent authority within 15 days, including the reasons for the premature termination.

Within one year after the end of the study, the investigator/sponsor will submit a final study report with the results of the study, including any publications/abstracts of the study, to the accredited EC and the Competent Authority.

15.5 Public disclosure and publication policy

The results of this trial will be disclosed unreservedly according to the rules of the CCMO statement on publication policy (www.ccmo.nl). If it cannot be published in peer reviewed journals, we will disclose the results to an international trial register (het Nederlands trial register: www.trialregister.nl and the EBMT database. The involved physicians will receive the draft of the manuscript to allow them to give their input. The order of the authors will be discussed in function of the amount of work given on each manuscript and the number of cases included.

APPENDIX A. ZUBROD-ECOG-WHO Performance Status Scale

- 0 Normal activity
- 1 Symptoms, but nearly ambulatory
- 2 Some bed time, but to be in bed less than 50% of normal daytime
- 3 Needs to be in bed more than 50% of normal daytime
- 4 Unable to get out of bed

APPENDIX B. NYHA* scoring list

Grade 1 No breathlessness

Grade 2 Breathlessness on severe exertion
Grade 3 Breathlessness on mild exertion

Grade 4 Breathlessness at rest

The *New York Heart Association functional and therapeutic classification applied to dyspnoea

APPENDIX C. Definitions of recovery, engraftment and chimerism

Neutrophil recovery: First of 2 consecutive days with neutrophils $\geq 0.5 \times 10^9$ /I

Platelet recovery: First of 2 consecutive days with platelets $\ge 20 \times 10^9$ /l without platelet support for 7 days

Engraftment: Neutrophil recovery in association with donor hematopoiesis > 10% in bone marrow

Primary graft failure: Cytopenia and marrow hypoplasia after 60 days with donor hematopoiesis < 10%

Secondary graft failure: Complete loss of donor hematopoiesis after initial engraftment.

Complete chimerism: >95% donor hematopoiesis, < 5% recipient hematopoiesis in bone marrow

Mixed chimerism: 10-95% donor hematopoiesis and >5% recipient hematopoiesis in bone marrow

Autologous reconstitution: >95% recipient hematopoiesis, < 5% donor hematopoiesis in bone marrow

